Purpose: The first part of our study will evaluate whether minimal support through weekly automated messaging helps people with MS adhere to a calorie restricted diet. It will also evaluate the effect of weight loss, particularly abdominal obesity, on fatigue and health-related quality of life in patients with MS. The second program will evaluate if shortening the period during the day in which people consume their typical food amounts leads to improvements in patient-reported outcomes or markers of metabolism.

Hypotheses: Intermittent reminders about the importance of adhering to a dietary intervention combined with use of a calorie-tracking smartphone application will improve adherence over use of the application alone. Weight loss, especially decreased abdominal obesity, will improve fatigue and quality of life in patients with MS. Even in people who are not reducing their calorie intake, consuming those calories within a shorter time period within each 24 hours will improve metabolic markers and patient-reported outcomes.

2. Objectives (include all primary and secondary objectives)

Primary Objective. To evaluate if automated messaging support helps people with MS adhere to calorie restriction diet. We predict that intermittent reminders about the importance of adhering to a dietary intervention combined with use of a calorie-tracking smartphone application that is intermittently shared with the study team, will lead to better adherence than use of the application alone in overweight and obese people with MS.

Secondary Objectives. A) To assess the effect of weight loss, particularly reduced abdominal obesity, on fatigue, health-related quality of life, and self-esteem in overweight and obese people with MS. Based on the current literature, we hypothesize that weight loss will improve these aspects of patient well-being.

B) To assess if shortening the time period in which typical calories are consumed during the day improves markers of metabolism, fatigue, or health-related quality of life in people with MS. We hypothesize that consolidating calories consumed into a shorter period of the day leads to improvements in metabolism and patient-reported outcomes.

1. Background

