Participants will then be randomized to one of two groups: 1) to receiving weekly educational text or email messages about the positive health effects of maintaining a normal body mass index, particularly as it relates to MS, or 2) standard of care (no additional contact). At the routinely-scheduled infusions at months 3 and 6, body mass index, waist circumference, and fatigue/HRQoL/self-esteem will be evaluated. Serum and plasma will be collected for future studies.

Enrollment and Randomization: In order to maximize enrollment within the period of support, people with MS who receive monthly natalizumab infusions and meet other criteria (see #3 inclusion/exclusion criteria) will be offered participation in the study. Potential participants may be notified when receiving their regularly scheduled appointment reminder phone call that a study team member may approach them during their upcoming infusion visit about enrollment in the study. The Johns Hopkins MS Center infusion center currently provides natalizumab infusions for

Date: 7/20/16

Principal Investigator: [name], MCR

Application Number: IRB00095554

140 MS patients per month; it is estimated that two-thirds have a body mass index ≥ 25 kg/m². Participants will be randomized by the study statistician 1:1 to the frequent patient activation arm or standard of care.

Study Procedures/Schedule of Events:

Patients will be consented one month prior to the baseline visit so they can be given adequate notice and can be given a stool sample collection kit to bring it at their next infusion. At the consent visit, baseline energy requirement will be determined (see below) and the patient's waist circumference will be measured. Waist circumference will be measured according to NIH protocol (patient standing with feet shoulder width apart, arms crossed over chest, and abdominal muscles relaxed, with measurement taken at the top of the iliac crest, at the end of normal expiration).

At the baseline visit, the following will be done:

- Vital signs and waist circumference
 - i. If waist circumference varies $\geq 10\%$ from the consent visit, baseline energy requirement will be re-calculated
- Patient-Determined Disease Steps

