Participants will receive education about two diet approaches: intermittent calorie restriction and continuous calorie restriction. For the intermittent calorie restriction group, a standardized percentage reduction to 25% of the baseline energy requirement will be used two days a week. For the continuous calorie restriction group, the same percentage calorie reduction will be provided, but the restriction will take place over an entire seven-day period (i.e. the group will be provided with food containing 78.6% of their baseline energy requirement (calories) each day. All participants will be encouraged to drink water liberally to stave off hunger. If a participant in one group is unable to follow their chosen diet, rather than losing the subject as a drop-out, the subject will switch to other dietary approach.

Adherence Intervention: All subjects will be asked to document adherence using the LoseIt! application, which tracks calorie intake based on food items and quantity consumed. The application will be installed on the subjects' smartphones at the baseline visit, and they will be instructed how to use it.

Subjects will be randomized 1:1, stratified by week of enrollment, to receive electronic adherence support or to the standard of care (no additional contact). The stratified randomization was chosen because participants often receive their infusions at the same time due to the 28-day dosing schedule, and thus may otherwise discuss their impressions of the study with other participants who happen to be infused at the same time. Those who are in the intervention arm will be sent a text message once a week providing encouraging information about the health benefits of weight loss and, where possible, specifically focusing on how it may benefit their MS. They will be asked to send the previous week's log of calories consumed to the research group (this information is readily available using the LoseIt! application).

Calorie Timing Study

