- Health-related quality of life (Functional Assessment in MS [FAMS]), fatigue (PROMIS fatigue), Pittsburgh Sleep Quality Index (PSQI), and physical activity (International Physical Activity Questionnaire) assessments
- Blood for future research
- Stool sample kit distribution (at month 3) and collection (at month 6)
- Collection of photographic data since prior visit

b. Study duration and number of study visits required of research participants.

The study duration is 6 months from the baseline visit. Follow-up visits will be done at the patients' scheduled infusion appointments at months 3 and 6.

c. Blinding, including justification for blinding or not blinding the trial, if applicable.

Subjects will be blinded to the study hypothesis that additional electronic support will help improve dietary adherence, which could influence and confound the results. Subjects will be told that the study is evaluating how easily changing calorie amounts or timing can be done in the real world and that, in addition to the baseline education, they may receive periodic contact from the study team via text message. For the calorie restriction study, both groups will receive reminder text messages about the month 3 and 6 study visits, which will help prevent unblinding. Further, the randomization strategy employed (clustered by week of baseline visit) will prevent contamination of patients who may discuss the study while getting infused, since the infusions are scheduled on an every 28-day basis and thus participants would co-mingle in the infusion center and may discuss their experience of the study. For the calorie timing study, participants will be sent text messages in the morning twice a week instructing them to capture

all foods and beverages they consume in the next 24 hours on their smartphone and to save those photos.

d. Justification of why participants will not receive routine care or will have current therapy stopped.

This study does not require any changes to the participants' medical therapies, and they will continue to receive routine care.

e. Justification for inclusion of a placebo or non-treatment group.

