For the primary objective, the impact of increased patient engagement via the smartphone on weight loss (pounds lost, change in body mass index, and change in waist circumference) as well as on the percentage adherence to the recommended calorie intake (as assessed by LoseIt! logs) will be evaluated in t-tests. If there are baseline imbalances in potentially meaningful covariates despite randomization, multivariate approaches accounting for imbalanced covariates will be employed.

For the secondary objective, the primary analysis will evaluate the association of weight loss (change in body mass index as well as change in waist circumference) with changes in health-related quality of life, sleep and fatigue using multivariate linear regression adjusted for age, sex, race, change in physical activity and baseline disability. Whether group assignment (extra smartphone engagement or standard of care) influences this relationship will also be evaluated.

The rationale for measuring change in waist circumference as the primary outcome is that waist circumference, rather than body mass index, is considered a better measure of the risk of metabolic syndrome.²⁰ However, for comparability with previously-published studies and in order to further evaluate the relationship between waist circumference with body mass index, both measures will be obtained.

Calorie Timing:

Metabolomics will be conducted on samples from the participants to evaluate the impact of restricting the hours in which foods are consumed. Primary analyses will be intent-to treat; secondary analyses will investigate with the actual time of day metrics, as assessed by time stamps of smartphone photos, are predictive of changes in metabolism. Secondary outcomes will be assessed as above.

d. Early stopping rules.

Participants who become pregnant, experience weight loss with BMI < 20 kg/m², or who develop another issue that, in the estimation of the investigator, puts them at risk of ongoing participation, the participant will be asked to cease following the diet but will be followed to the completion of the study.

6. Risks

a. Medical risks, listing all procedures, their major and minor risks and expected frequency.

- Calorie-restriction diet
 - The risks associated with the diets are not known
 - Previous studies of similar diets in humans have not shown any serious risks.
 -

-
- Calorie timing diet
 - Participants may be hungrier in the time in which foods are not being consumed

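### The main regression of well-being on weight loss (Secondary Objective A) leaves out randomised arm, so part of any between-arm difference in self-report may be credited to weight loss

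*Combined protocol and SAP*

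**What the plan says.** The calorie restriction study offers enrolment to 80 overweight or obese patients and randomises 1:1. Under Adherence Intervention (Study Procedures, 2a), the support arm gets a weekly text "providing encouraging information about the health benefits of weight loss and, where possible, specifically focusing on how it may benefit their MS". The Overview in the same section describes the content as "the positive health effects of maintaining a normal body mass index, particularly as it relates to MS". The comparator gets standard of care without this contact; section 2c adds that both arms receive reminders of the month 3 and month 6 visits.

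The Primary Objective predicts better adherence in the support arm, and section 5c compares weight loss between arms under that objective. Secondary Objective A concerns fatigue, quality of life and self-esteem: "we hypothesize that weight loss will improve these aspects of patient well-being". For it, the main analysis in 5c relates BMI change and waist change to change in fatigue, sleep and quality of life, and is to be done "using multivariate linear regression adjusted for age, sex, race, change in physical activity and baseline disability". The next sentence reads: "Whether group assignment (extra smartphone engagement or standard of care) influences this relationship will also be evaluated". No model is given for that further step.

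On blinding, 2c states: "Subjects will be blinded to the study hypothesis that additional electronic support will help improve dietary adherence". The reason given is that knowing this could distort the results.

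**The concern.** Arm is intended to change the exposure in this regression (weight loss). It may also change the outcomes directly. Quality of life, fatigue and sleep are measured by questionnaire (FAMS, PROMIS fatigue, PSQI), and one arm alone is told every week that losing weight is good for health and, where possible, for MS. Expectation, or simply regular contact, could move those answers without any weight being lost. A variable that affects both exposure and outcome confounds the association when it is left out. Here it is known for every participant and is the trial's own randomised factor.

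At stake is the reading of the main Secondary Objective A slope. If the messages raise weight loss and improve self-report directly, the pooled slope leans in the direction the trial predicts.

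**Working it through.** The documents state no alpha, power, SD or effect size, so there is no figure of theirs to reproduce. From the documents: 80 participants at 1:1, taken as 40 per arm with no dropout; arm not among the listed covariates. Assumed: the two arm effects, a two-sided 5% test, independent participants, the other covariates ignored, and scores oriented so that higher is better.

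**Formula.** Let d be the arm difference in weight loss, g the direct arm shift in the score, and s the within-arm SD of weight loss. With 1:1 allocation the arm indicator has variance 0.25. If weight loss has no true effect, the covariance of loss and score is 0.25·g·d and the variance of loss is s² + 0.25·d². The slope without arm therefore has

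bias = 0.25·g·d / (s² + 0.25·d²).

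It is zero when d = 0 or g = 0.

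**In SD units (s = 1),** with 20,000 simulated trials per row and a true slope of zero:

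| d | g | bias by formula | false positives, arm omitted |
|---|---|---|---|
| 0 | 0.5 | 0 | 4.9% |
| 0.2 | 0.3 | 0.015/1.01 = 0.015 | 5.0% |
| 0.5 | 0.3 | 0.0375/1.0625 = 0.035 | 6.3% |
| 0.5 | 0.5 | 0.0625/1.0625 = 0.059 | 8.3% |
| 0.8 | 0.5 | 0.10/1.16 = 0.086 | 12.3% |
| 0.8 | 0.8 | 0.16/1.16 = 0.138 | 23.5% |

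With arm added as a main effect, the bias is about zero and false positives are 4.7% to 5.2% in every scenario. For scale, the slope's standard error is about 1/√80 = 0.11.

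**Is d of this size plausible?** With 40 per arm, the difference detectable with 80% power is (1.96 + 0.84)·√(2/40) = 0.63 SD. A message effect that the arm comparison of weight loss could reliably detect is thus in the range where the bias begins to count, provided g is large too.

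**In centimetres,** with an assumed s = 5 cm, d from 2 to 5 cm and g from 2 to 5 points on an unspecified scale:

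- (d, g) = (2, 2): 1/26 = 0.04 points per cm
- (3, 3): 2.25/27.25 = 0.08
- (5, 3): 3.75/31.25 = 0.12
- (3, 5): 3.75/27.25 = 0.14
- (5, 5): 6.25/31.25 = 0.20

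The range is 0.04 to 0.20 points per cm, or 0.2 to 1.0 point for a 5 cm loss.

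**What adding arm does not remove.** Suppose expectation in the message arm grows with the participant's own weight loss (score = k × arm × loss). With k = 0.3 and d = 0.5 the slope is 0.158 without arm and 0.149 with it.

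**Price in precision.** Adding arm removes the between-arm part of the variance of weight loss: 0.0625/1.0625 = 6% at d = 0.5 and 0.16/1.16 = 14% at d = 0.8. For the same residual variance the standard error rises by a factor of √1.0625 = 1.03 or √1.16 = 1.08.

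**The case against.** The strongest reply is that 5c does bring group in, in the very next sentence. The usual model for that question contains arm and an arm-by-weight-loss term, or fits the arms separately, and either gives within-arm slopes. This stands in part: a reader might infer that the plan ignores arm, and it does not. But the sentence reads as an added question about effect modification, names no model, and leaves the main slope unadjusted.

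Second, the bias needs two unverified effects at once. This stands. At 0.5 and 0.5 SD the bias is about half a standard error (0.059 against 0.11), and at smaller values it is negligible.

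Third, adjusting for arm discards the only randomised variation in weight loss. This is true and is a real trade-off. That variation helps only if the messages affect well-being through weight loss alone, which is the point in doubt, and under the assumed values it is only 6% to 14% of the total.

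Three stronger readings are tempting but unsupported:

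- That the messages state the Secondary Objective A hypothesis. The message texts are not in the document; the descriptions mention health, normal BMI and MS, not fatigue, quality of life or sleep.
- That 2c exposes the well-being hypothesis. It conceals only the support hypothesis expressly, but the account it gives participants concerns how practicable dietary change is and discloses nothing about well-being.
- That self-esteem is affected in this regression. It is in the objective but not among the outcomes named for the model.

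**Conclusion.** The point holds as a conditional one. The main Secondary Objective A model omits a variable that the trial expects to drive weight loss and that may also shift self-report, so the pooled slope may credit part of a between-arm difference to weight loss. A reader might infer that it certainly does; the documents do not support that, because neither arm effect is known and the bias vanishes if either is absent. On assumed values it is small at modest effects and becomes material when both reach about 0.5 SD. It concerns a secondary objective, and the change is cheap enough to be worth making before analysis.

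**What to change.** In 5c, include randomised arm as a prespecified main-effect covariate in the main Secondary Objective A regression. Define the later group evaluation as an arm-by-weight-loss interaction.

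The cost is one degree of freedom with 80 participants and, on the values above, a standard error about 3% to 8% larger. The slope then rests on within-arm variation in weight loss and should be reported as observational. Expectation that follows a participant's own weight loss remains and should be stated as a limitation.

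Restricting what the messages may say is not recommended for this purpose: their MS-specific content is part of the intervention tested under the Primary Objective, and changing it to protect a secondary association would alter that test.

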Dietary modification represents an intriguing potential MS intervention. **One aspect of diet that shows promise involves calorie intake.** Calorie restriction or fasting prior to the induction of experimental autoimmune encephalomyelitis (EAE), a mouse model of MS, is associated with a less aggressive course.^{11,12} There may be several mechanisms by which this occurs. **Calorie restriction and fasting are associated with reductions in pro-inflammatory cytokines** and other inflammatory markers in EAE mice^{11,12} and in humans who are healthy, obese, or have asthma, similar reductions have been observed.¹³⁻¹⁶ Ceramides are elevated in MS patients and pathogenic in vitro;¹⁷ calorie restriction reduces their levels in humans without MS.¹⁵ Calorie restriction also reduces markers of oxidative stress,¹⁵ and thus may reduce mitochondrial dysfunction. Beyond its direct biological effects, optimization of weight may lead to improvements in MS-related symptoms such as fatigue as well as in health-related quality of life, as overweight MS patients have been shown to have lower self-rated measures of well-being than controls.^{18,19} As such, **there is a strong rationale for evaluating the benefits of calorie restriction in MS.** The timing of calorie intake may also be critical, suggesting a possible rationale for consolidating the time period in which typical calories are consumed.

2. Study Procedures

a. Study design, including the sequence and timing of study procedures

Calorie restriction study:

Overview: We will conduct a pragmatic pilot study in which 80 patients with MS who are undergoing monthly infusions with natalizumab and who are overweight or obese are offered enrollment in this trial. Participants who consent will undergo a basic evaluation of total energy expenditure. At baseline, participants will participate in a short training about intermittent versus continuous calorie restriction and will choose the dietary intervention they'd prefer to use. The LoseIt! Application will be installed on the participants' smartphones, and they will receive training in utilizing the application. Baseline assessments of health-related quality of life (HRQoL), fatigue, self-esteem and physical activity will be conducted. Serum and plasma will be collected for future studies.

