- Health-related quality of life, (Functional Assessment in MS [FAMS]), fatigue (PROMIS fatigue), Pittsburgh Sleep Quality Index (PSQI), timing of sleep (Morningness-Eveningness Questionnaire [MEQ]), self-esteem (Rosenberg Self-Esteem Scale) and physical activity (International Physical Activity Questionnaire) assessments
- Blood for future research collected (30 ml)
- Coaching about the two diet options
- Installation of LoseIt! application on smartphone
- Determination of baseline energy requirement (*see below*)
- Randomization group assigned (participant blinded)
- Stool sample kit collection

At follow-up visits (months 3 and 6), the following will be done:

- Vital signs and waist circumference
- Patient-Determined Disease Steps (month 6 only)
- Health-related quality of life (Functional Assessment in MS [FAMS]), fatigue (PROMIS fatigue), Pittsburgh Sleep Quality Index (PSQI), timing of sleep (Morningness-Eveningness Questionnaire [MEQ]), self-esteem (Rosenberg Self-Esteem Scale) and physical activity (International Physical Activity Questionnaire) assessments
- Blood for future research (30 ml/visit)
- Stool sample kit distribution (at month 3) and collection (at month 6)
- Collection of LoseIt! application data (calorie counts) since prior visit

Determination of Baseline Energy Requirement and Diet Details: The baseline energy requirement (total energy expenditure) of each participant will be determined prior to randomization. This measurement is defined as the number of calories needed to maintain the current body weight. Total energy expenditure will be assessed using validated equations from University of Arizona Calorie Need Estimates, which include an individual's estimated resting

Date: 7/20/16

Principal Investigator: [name], MCR

Application Number: IRB00095554

energy expenditure (based on current weight, height and age) and physical activity (based on the International Physical Activity Questionnaire short form).

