Age 18-75 years; meets 2010 criteria for MS	To ensure broadly generalizable to the MS patient population
Body mass index (BMI) < 25 kg/m ² , or if higher, participant was unwilling to enroll in calorie restriction study	Only want to enroll overweight or obese individuals if they are unwilling to restrict calories, as calorie timing study unlikely to lead to weight loss
No history of diabetes requiring medication	To avoid unpredictable hypoglycemia
Not pregnant, willing to avoid becoming pregnant during the study, and not breastfeeding	To avoid danger to fetus or threats to milk supply or health
No history of an eating disorder	To prevent relapse of eating disorder
No current use of warfarin	To avoid INR fluctuations
No history of major surgery within past 3 months	To prevent improper wound healing
Have a smart phone with the capability of taking and storing photographs	To provides study team with time stamps indicating timing of oral intake.

4. Drugs/ Substances/ Devices

- a. The rationale for choosing the drug and dose or for choosing the device to be used. N/A
- b. Justification and safety information if FDA approved drugs will be administered for non-FDA approved indications or if doses or routes of administration or participant populations are changed. N/A
- c. Justification and safety information if non-FDA approved drugs without an IND will be administered. N/A

5. Study Statistics

a. Primary outcome variable.

Calorie restriction study: Change in waist circumference

Calorie timing study: Change in metabolism biomarkers

b. Secondary outcome variables.

Calorie restriction study: Change in body mass index, number of pounds lost, percentage adherence to recommended calorie intake, changes in health-related quality of life, changes in fatigue and sleep

Calorie timing study: Adherence to photographing foods, changes in health-related quality of life, fatigue, and sleep

c. Statistical plan including sample size justification and interim data analysis.

Summary statistics (mean \pm standard deviation, median and interquartile range, or number and percentages) will be used to describe the outcomes.

Calorie Restriction:

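### Calorie restriction study: the primary objective is diet adherence, the primary outcome is waist circumference, section 5c gives four t-tests to that objective, and no primary visit is named

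*Combined protocol and SAP*

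**What the plan says.** The Objectives section opens with "Primary Objective. To evaluate if automated messaging support helps people with MS adhere to calorie restriction diet" and predicts better adherence with messaging than with the application alone. Section 2c (Blinding) describes the hypothesis kept from participants as one about dietary adherence. Section 2e justifies the untreated group by the need to compare adherence between arms.

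Section 5a gives the primary outcome as "Calorie restriction study: Change in waist circumference". Section 5b lists percentage adherence among the secondary outcomes, with BMI change and pounds lost. Section 5c says that, for the primary objective, the effect of messaging on pounds lost, BMI change, waist change and percentage adherence will be assessed by t-tests. Two paragraphs later, 5c defends waist circumference as the primary outcome because it reflects metabolic-syndrome risk better than BMI does.

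Vital signs and waist are recorded at months 3 and 6. The Schedule of Events specifies the technique ("Waist circumference will be measured according to NIH protocol"). Adherence data come from the participant's phone: "Collection of LoseIt! application data (calorie counts) since prior visit". In the messaging arm only, participants receive a weekly message and "They will be asked to send the previous week's log of calories consumed to the research group". The study is described thus: "We will conduct a pragmatic pilot study in which 80 patients with MS". Allocation is 1:1, so 40 per arm if all 80 are randomized.

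**The concern.** A primary outcome should be the measurement that answers the primary objective. Here it is not. In the objectives, abdominal obesity appears only in Secondary Objective A, as the factor whose effect on fatigue, quality of life and self-esteem is studied. The reason given in 5c for choosing waist compares it with BMI. It does not connect waist to adherence or explain why adherence was ranked below it.

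The two measures can disagree. One is self-logged intake and the other is a body measurement taken at a visit. If messaging improves logged adherence but waist does not change, the Objectives section points to one answer and 5a to another; the opposite pattern reverses the two. Section 5c does not settle the matter, because it places both outcomes and two more under the same objective, with no order and no alpha. The unnamed visit leaves a second choice open even for a reader who takes waist as primary.

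**Working it through.** **Step 1. Set the sections side by side.**

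| Place | What it treats as primary |
|---|---|
| Objectives, Primary Objective | adherence |
| 2c, concealed hypothesis | adherence |
| 2e, reason for control group | adherence |
| 5a, primary outcome | waist change |
| 5b | adherence, BMI change and pounds lost are secondary |
| 5c, tests for the primary objective | pounds lost, BMI, waist, adherence |
| 5c, rationale | waist change |

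The outcomes are ranked, and 5a agrees with the 5c rationale. That ranking does not match the objective, and the list of tests in 5c does not match the ranking.

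**Step 2. Look for the visit.** Sections 5a and 5c name none. Section 2b gives a duration of 6 months from the baseline visit, with follow-up at months 3 and 6. Month 6 is a reasonable inference, but it is not stated. Adherence is not a single-visit measurement: logs are collected for the time since the previous visit, so months 0-3, 3-6 or 0-6 could each be scored.

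**Step 3. What a choice after the fact could cost.** The documents state no alpha; assume two-sided 0.05 per test. A choice between two candidates (waist at month 3 or month 6, or waist versus adherence at one time point) gives 1 − 0.95² = 9.75% if they are independent. For waist at either visit, assumed between-visit correlations of 0.5 to 0.9 bring this to about 7%-9%. A choice among the four outcomes at one time point gives 1 − 0.95⁴ = 18.5% if independent, and about 10%-15% under assumed correlations (pounds with BMI 0.95-0.99, weight with waist 0.5-0.9, adherence with the others 0.2-0.7). With one outcome at one time point it is 5%.

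**Step 4. Why the two ways of aligning the text differ.** Only the messaging arm is asked to send logs weekly, so the intervention may change logging itself. The documents do not say how an unlogged day is scored. Assume that messaging has no effect on eating, 40 per arm, individual randomization, no dropout, a mean share of days logged of 0.60 in controls and 0.60, 0.65 or 0.70 with messaging (SD 0.20 or 0.25), and mean adherence on logged days of 0.5 or 0.7 in both arms (SD 0.20).

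- *Unlogged days count as non-adherent.* Score = share logged × adherence on logged days. Expected difference for +5 points of logging: 0.05 × 0.5 = 2.5 points to 0.05 × 0.7 = 3.5 points. For +10 points: 0.10 × 0.5 = 5.0 to 0.10 × 0.7 = 7.0 points. In 20,000 simulated trials per setting, a two-sided 0.05 t-test rejected in about 5% with equal logging, 9%-13% at +5 points and 22%-35% at +10 points.
- *Check of the top value (logging SD 0.20, adherence mean 0.7).* Control variance: (0.60² + 0.20²)(0.70² + 0.20²) − 0.42² = 0.40 × 0.53 − 0.1764 = 0.0356. Messaging variance: 0.53 × 0.53 − 0.49² = 0.0408. Standard error: √((0.0356 + 0.0408)/40) = 0.0437. Ratio: 0.07/0.0437 = 1.60. The noncentral t with 78 degrees of freedom gives a rejection probability of 0.353.
- *Only logged days are scored.* Under the same inputs, rejection stays at about 5% (0.048-0.054).

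So the range for percentage adherence as written is about 5% to 35%, and the scoring rule determines where in that range the test falls.

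**The case against.** The strongest reply is that the plan does have a single primary outcome. Sections 5a and 5c both name waist, and 5b labels the other three as secondary. If that hierarchy governs, the four-test figures in Step 3 fall away. This is fair, and it is why the point is one of alignment rather than of a missing hierarchy. It does not make waist an answer to a question about adherence, and it does not name the visit.

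Second, this is a pilot and all four outcomes are tested whichever label applies. That lowers the weight of formal error control. A reader might go further and infer that the trial would be declared a success under one section and a failure under another. The documents state no success criterion, so they do not support that; what is at risk is the meaning of the word primary.

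Third, a reader might multiply four outcomes by two visits and report eight tests of the primary objective. No section says that the t-tests are run at both visits, and adherence is scored over a period, so that count is not in the documents.

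Fourth, waist is also measured at consent: "At the consent visit, baseline energy requirement will be determined (see below) and the patient's waist circumference will be measured". A reader might infer that the reference value is unclear. The consent value has its own use (deciding whether to recalculate energy need), and section 2b counts follow-up from a named baseline visit, so little ambiguity remains.

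Fifth, the logging illustration might be read as showing that adherence cannot be the primary outcome. It does not: scoring logged days only removes the inflation under these inputs. Nor is waist free of questions. The plan gives the technique, but not who measures or whether that person is blinded.

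**Conclusion.** The point holds and should be fixed before analysis. The objective, concealed hypothesis and control-group rationale concern adherence; the primary outcome is waist change; 5c attaches four tests to the primary objective; and the primary time point is not stated. These are readings of the text and need no assumption.

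No analysis is lost. The consequence is that the result answering the primary objective is ambiguous and could be chosen after the data are seen. The error rates for such a choice rest on an assumed 0.05 per test and assumed correlations, and apply only if a choice is actually made. The 5%-35% range for adherence rests on assumed logging and adherence distributions and on a scoring rule that the plan does not give. It bears on which remedy to choose; it does not measure the mismatch itself.

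**What to change.** Align the objective and the primary outcome by one of two routes.

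(a) Keep waist change primary. Reword the Primary Objective as the effect of messaging, added to the application, on abdominal obesity, and make percentage adherence a named key secondary outcome. This needs edits to the abstract (Purpose and Hypotheses), Objectives, 2c, 2e and 5a-5c, and a check of the other adherence-based text (the abstract background, the smartphone eligibility rationale and Benefits). It needs no new data. The cost is that the question that motivated the trial is tested only as secondary.

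(b) Make percentage adherence primary. Give one definition for both arms, a rule for unlogged days and a scoring period. Say whether the score is daily or weekly, because "the subject will switch to other dietary approach" when the chosen diet cannot be followed. The two diets share a weekly target, (2 × 25% + 5 × 100%)/7 = 78.6% of baseline energy per day on average, but not a daily one. Sections 5a-5c change accordingly. The cost is that a common definition does not remove logging differences caused by the weekly request, so the share of days logged should be reported by arm.

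Under either route, name one primary time point (for example month 6, or one scoring period for adherence) and one alpha. Let 5c assign only that test to the primary objective. Label the other outcomes and the other visit secondary, and report them with confidence intervals. The cost is that an isolated positive result elsewhere could not be presented as the primary finding.
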